12.7.1 Reporting Abnormal Nerve Function Monitoring

If the investigator observes any worsening of NFM assessments compared to the subject’s status prior to administration of study drug (subject total Before Treatment status is calculated as the average of the Screening visit and Baseline visit data), they will complete a checklist with a set of additional standard questions that may explain the observation, and inform the ICON MM ([contact]). The subject will continue to receive study drug.

The ICON MM will review the data for this subject within 1 business day and decide whether the event fulfils the criteria of a potential nerve safety signal (i.e. at least two related NFM parameters affected AND no other plausible explanation available). If classified as a potential nerve safety signal, this will be escalated to the DSMB Nerve Function Monitoring sub-committee, as per communication flow and according to timelines detailed in the DSMB Charter. If the event does not fulfil the criteria, the site is informed and the case is closed.

One member of the DSMB Nerve Function Monitoring sub-committee will review the package (in an unblinded fashion) and conclude within two business days whether the finding is:

- a) Confirmed: If Confirmed, the ICON MM is informed and will initiate a stop of dosing of the subject. The case is also escalated to the full DSMB to decide whether the study can progress as planned.
- b) Not confirmed: If Not confirmed, the DSMB Nerve Function Monitoring sub-committee needs to instruct the site, in a blinded manner (via the ICON MM), what additional measures are needed, e.g. to repeat the neurography, include other nerves in the assessment, etc.
- c) Artefact/existing event: If classified as an artefact/existing event, the case is closed and the subject will continue in the study as planned.

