9.5 Withdrawal of Subjects

Subjects may withdraw from the study at any time at their own request, or they may be withdrawn at any time at the discretion of the investigator or sponsor for safety, behavioural, or administrative reasons. The decision to withdraw consent and discontinue participation in the study will not prejudice the subject’s future medical treatment in any way. If a subject

does not return for a scheduled visit, every effort will be made to contact the subject. In any circumstance, every effort will be made to document subject outcome, if possible. The investigator should inquire about the reason for withdrawal, and request the subject to return for the EOT (Week 12) visit, if applicable, and follow-up with the subject regarding any unresolved AEs (for details see [Section 12.1.1.1](#)). The investigator or sub-investigator will be responsible for reporting subject withdrawal to Actinogen Medical/ICON. Subjects withdrawn from the study cannot be re-enrolled at a later time, regardless of the reason for withdrawal.

If a subject consents to undertake additional and optional study procedures/assessments but withdraws consent for doing so at a later visit, he/she will be retained in the study for the routine study procedures/assessments. If a subject withdraws from the study, and also withdraws consent for disclosure of future information, no additional data should be collected. Actinogen Medical/ICON may retain and continue to use any data collected before such withdrawal of consent.

Subjects shall be withdrawn during the course of the study when subject well-being is at risk, including but not limited to:

- Subject needs to take a prohibited medication. In case medication from the list of drugs potentially prolonging QTc (Appendix III) is introduced, the most appropriate approach will be discussed upfront with the ICON MM since the subject may not need to be withdrawn in all cases, e.g. in situations where the new drug is only provided temporarily, or in low doses, or in situations where baseline QTc was in the lower range of normal.
- ECG indicates a QTc level above a threshold of 480 msec at the Interim (Week 4 and Week 8) visits or an increase in QTc from Baseline > 60 msec (for details see [Section 12.3](#)). In this case, it should be reported as an AESI, within 24 hours.
- Subject develops signs or symptoms of peripheral neuropathy in any two tests of NFM, confirmed by the DSMB Nerve Function Monitoring sub-committee.

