In order not to disseminate unblinded data and to ensure that all staff involved in the conduct and final analysis of the study remain blind to the data, only the members of the DSMB, the DSMB Nerve Function Monitoring sub-committee and the unblinded DSMB statistician will have access to these data.

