15.2.4.1 Data Safety Monitoring Board Nerve Function Monitoring Sub-committee

The DSMB Nerve Function Monitoring sub-committee consists of two experts in neurophysiology, one of which will be the DSMB Chairperson. The unblinded NFM data will be primarily reviewed by the DSMB Nerve Function Monitoring sub-committee. When

there is a confirmed nerve safety signal, this is escalated to the DSMB for consideration and recommendations for the study. Further details will be provided in the DSMB Charter.

For quality control measures, the results of neurography of one subject per study site will be reviewed by a member of the DSMB Nerve Function Monitoring sub-committee. The study site will complete a Neurography Screening Quality Control Form and send it to the ICON MM. The study site may, however, proceed with subject randomisation if all eligibility criteria are fulfilled.

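### One reviewer with the treatment code open classifies each potential nerve safety signal, with no masked read described first, so dosing stops and withdrawals can depend on knowledge of treatment

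*Protocol*

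**What the plan says.** Protocol 12.7.1 sets out two steps. The medical monitor first decides whether a worsening in nerve function monitoring (NFM) is a potential nerve safety signal, using a stated criterion: "at least two related NFM parameters affected AND no other plausible explanation available". Cases that pass go to the NFM sub-committee of the DSMB, where "One member of the DSMB Nerve Function Monitoring sub-committee will review the package (in an unblinded fashion) and conclude within two business days" which of three categories applies.

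The consequences differ by category:

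- Confirmed: "If Confirmed, the ICON MM is informed and will initiate a stop of dosing of the subject", and the case goes to the full DSMB, which decides whether the study can go on.
- Not confirmed: the site is told, blinded and through the medical monitor, what further measurements are needed.
- Artefact: "If classified as an artefact/existing event, the case is closed and the subject will continue in the study as planned".

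Protocol 9.5 lists as a ground for withdrawal: "Subject develops signs or symptoms of peripheral neuropathy in any two tests of NFM, confirmed by the DSMB Nerve Function Monitoring sub-committee". Section 15.2.4.1 says that the sub-committee "consists of two experts in neurophysiology, one of which will be the DSMB Chairperson". Section 15.2.4 limits unblinded access to the DSMB, this sub-committee and the unblinded DSMB statistician; the stated aim is "to ensure that all staff involved in the conduct and final analysis of the study remain blind to the data". The medical monitor is not on that list. Further procedure is left to the DSMB Charter.

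**The concern.** A safety board needs unblinded data to compare arms. Deciding whether one subject's finding is real or an artefact is a different task, and it does not need the arm. The inputs leave room for judgement: local equipment and local normal values, back-up nerves, two thermal methods across sites, and subject-reported symptoms (Protocol 12.7, 12.8). A reviewer who can see the allocation may lean towards confirming on active and towards artefact on placebo, or the reverse.

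The first leaning would lose what the placebo arm is there to show, namely how often this monitoring raises false alarms. The opposite leaning could hide a real effect. Because the verdict leads directly to a dosing stop, a ground for withdrawal and escalation, any leaning passes into those decisions. Nothing recorded in the described process would later show whether it had happened.

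**Working it through.** **Which outputs use the verdict**

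- Dosing stop and escalation (Protocol 12.7.1) and withdrawal (9.5): directly.
- By-arm tables of treatment-emergent adverse events leading to stopping study drug or leaving the study (Protocol 15.2.3.7, SAP 7.8.1), and disposition (SAP 7.1): through those stops and withdrawals.
- The DSMB's view of confirmed cases: directly.
- Planned NFM summaries of NTSS-6, TCNS and neurography, with counts of NTSS-6 above 6 and abnormal sensory tests (Protocol 15.2.3.7, SAP 7.8.4.1 to 7.8.4.3): no. They are built on measurements from blinded sites.
- Adverse events of special interest: no. Protocol 12.1.1 sets the NFM event at the potential-signal stage, before the code is opened.
- Week 12 efficacy data: only indirectly, if a stop or withdrawal leads to a missed assessment.

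**The plan's own figures** (Protocol 15.1, 78 subjects per arm). The probability of at least one case is 1 − (1 − p)^78.

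- p = 3%: 1 − 0.97^78 = 0.907. The protocol says about 90%.
- p = 5%: 1 − 0.95^78 = 0.982. The protocol says more than 98%.

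Both reproduce.

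**Size of a possible leaning.** Assume that the 3% and 5% rates apply to signals reaching the reviewer and are equal in both arms, so there is no drug effect. Expected signals per arm are 78 × 0.03 = 2.34 and 78 × 0.05 = 3.90. The confirmation rates below are assumptions; the documents give none.

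| Signal rate | Signals per arm | Confirmed, active at 60% | Confirmed, placebo at 30% | Difference |
|---|---|---|---|---|
| 3% | 2.34 | 1.40 | 0.70 | 0.70 |
| 5% | 3.90 | 2.34 | 1.17 | 1.17 |

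Other assumed leanings, as expected confirmed cases on active versus placebo:

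- 90% versus 70%: 2.11 versus 1.64 at the 3% rate, and 3.51 versus 2.73 at the 5% rate.
- 90% versus 50%: 2.11 versus 1.17, and 3.51 versus 1.95.
- 50% versus 90%, the opposite leaning, at the 5% rate: 1.95 versus 3.51.
- Equal confirmation rates in both arms: difference zero.

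**Who confirms.** Section 9.5 assigns confirmation to the sub-committee, which 15.2.4.1 says has two experts. Section 12.7.1 lets one member conclude. Neither section says how the two fit together.

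**The case against.** The unblinded review is deliberate, and the step before it is protected: the medical monitor, not listed as unblinded, applies a written criterion, and that earlier classification already reaches a by-arm table as an adverse event of special interest. This stands and limits the reach of the point. It does not replace the three-way category, which is decided later with the code open and is what drives the stop.

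The Charter may contain a masked read. That also stands as a limit: the gap can be stated only for the protocol and SAP. But 12.7.1 as written directs an unblinded review.

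Three stronger readings are tempting, and the documents do not support them.

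- A reader might infer that a planned comparison of confirmed neuropathy between arms is biased. Neither document plans one.
- A reader might infer that the primary analysis is compromised, since it does not replace missing Week 12 values. The path is indirect. Subjects who stop early have the end-of-treatment assessments if possible (Protocol Table 1 footnote 2, 9.4.1.6), withdrawn subjects are asked back for that visit (9.5), and SAP 7.7.1.1 adds placebo-based and missing-at-random sensitivity analyses. Some arm-dependent missingness could remain.
- A reader might infer that a confirmed verdict unblinds the medical monitor. A confirmed nerve finding may suggest active drug even when read masked, and neither document gives this role any part in rating efficacy.

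**Conclusion.** The point holds in limited form. As the protocol and SAP stand, one reviewer who can see the allocation makes the classification, with no masked read or category criteria described. Dosing stops, withdrawals, discontinuation and disposition tables, and the DSMB's picture of confirmed cases can therefore depend on knowledge of treatment.

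Under the 60% versus 30% assumption the expected excess is about 0.7 to 1.2 active-arm confirmations. That is small in number, but it is set against only 2.3 to 3.9 expected signals per arm. The figure rests on assumed confirmation rates and on reading the 3% to 5% planning rates as signal rates. The real bias is unknown, could run either way and may be zero; the process described leaves no record from which to tell.

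This is a cheap improvement, not a flaw that undermines the planned safety summaries or the primary analysis. The mismatch between 9.5 and 12.7.1 on who confirms needs no assumption about bias and must be reconciled in any case.

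**What to change.** - In Protocol 12.7.1 and the DSMB Charter: the same sub-committee member first classifies the package masked to treatment and records the category with a time stamp. The code is opened afterwards, within the same two-business-day limit, for escalation to the DSMB. Any later change of category is documented with its reason.
- The sponsor states which recorded classification, masked or later, the existing consequences in 12.7.1 attach to. Otherwise a change made after the code is opened could bring back the same dependence.
- In the SAP: tabulate the masked classification by arm.
- Reconcile 9.5 with 12.7.1 on whether the sub-committee or one member confirms.

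No clinical stopping rule is proposed, and the DSMB loses no access. The cost is short text changes in the protocol, Charter and SAP, one extra form field, one added table, and a review package prepared without the treatment code.

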12.8 Neuropathy Total Symptom Score-6

The six questions of NTSS-6 should be completed as part of the assessment of subjects' medical history, also asking for input from the caregiver to make sure no information is lost. Each item will also be graded for its frequency and intensity, adding up to a total score from "0" to "21.96" points. A total score of > 6 would exclude the subject from the study.

12.9 Columbia Suicide Severity Rating Scale

The CSSRS was initially designed to assess suicidal ideation and behaviour in clinical studies³⁹. Psychometric analysis of data on adolescents indicated that a lifetime history of worst-point suicidal ideation including either suicidal intent or intent with a plan, predicts a future risk of an actual attempt that is four times as great as the risk associated with a history of current suicidal ideation including a desire to be dead or increased general ratings of depression. The CSSRS demonstrated good convergent and divergent validity with other multi-informant suicidal ideation and behaviour scales and had high sensitivity and specificity for suicidal behaviour classifications compared with another behaviour scale and an independent suicide evaluation board.

The CSSRS is frequently asked for or recommended by various international agencies such as the FDA or World Health Organisation. The CSSRS has been administered numerous times and has exhibited excellent feasibility – no mental health training is required to administer it.

13 PHARMACOKINETIC AND PHARMACODYNAMIC ASSESSMENT

PK and PD assessments will include:

- **PK assessment.** PK results are blinded and will not be provided to the sites or the subjects.
 - Each participating subject will provide one blood sample between 3 to 5 hours post-dose at the Baseline (Week 0) visit and two blood samples (pre- and post-dose) at each of the Interim visits (Week 4 and Week 8) and one sample at the EOT (Week 12) visit. The first sample is a trough sample and will be taken on arrival at the study site, from subjects in a fasted state, before dosing. The second sample will be taken between 3 to 5 hours post-dose, around the time anticipated peak concentrations occur. The exact time of sampling, plus the exact time of study drug intake on that day and the previous day, and the time of food intake must be documented.
 - The study site shall remind participating study subjects to write down the exact time-point when study drug was taken each day, in the Drug Intake Diary, between all study visits up to the EOT (Week 12) visit.
 - Subjects who cannot provide a documented time-point for study drug intake for the 24 hours prior to the visit will not undergo PK sampling. They will be reminded to properly document the time of study drug intake for the next visit. Another attempt for PK sampling will then be made.
 - PK blood samples will be analysed for concentrations of Xanamem™ by a validated liquid chromatography–mass spectrometry method. Data collection and standard curve regression will be performed using Analyst® software from AB Sciex. Only active treatment samples will be analysed. It should be noted that the randomisation code will be provided to ICON Bioanalytical Laboratory to exclude placebo samples for PK analysis. In no case will this code list be made known to the study investigators or the monitors. Xanamem™ concentrations will not be disclosed to the study site due to the unblinding potential. After the database lock and unblinding of the study, the PK data will be delivered within ICON for PK analysis.
 - PK blood samples will be analysed for cortisol levels by the secondary clinical laboratory in a blinded fashion.
- **Optional PD assessment.** Samples for the determination of ACTH, DHEAS, androstenedione and testosterone will be taken from a sub-population of approximately 50 subjects enrolled into the main study, who also volunteer to take part in the PD sub-study, unless a higher number is defined as a result of the analysis of the data from those subjects, by the DSMB. Subjects who cannot provide a PK sample will not undergo PD sampling. Another attempt for PD sampling will be made at the next visit. The objective of this is to assess the impact of Xanamem™ on the hypothalamic-pituitary-adrenal axis. The sample must be taken pre-dose (as early as possible in the morning). For optimal results, the sample for androstenedione analysis

should be taken between 6 am and 10 am. PD results are blinded and will not be provided to the sites or the subjects; results will not be disclosed to study sites to avoid unintended subject treatment unblinding.

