8.5 Pharmacokinetics/Pharmacodynamics

- **PK assessment:** PK blood samples will be taken from all enrolled subjects.
- **Optional PD assessment:** PD blood samples will be taken from approximately 50 subjects enrolled into the main study who also volunteer to take part in the PD sub-study, unless a higher number is defined as a result of the analysis of the PD data, by the Data Safety Monitoring Board (DSMB). Samples will be taken pre-dose from subjects in a fasted state, to evaluate the adrenocorticotrophic hormone (ACTH), dehydroepiandrosterone sulfate (DHEAS), androstenedione and testosterone at the Baseline (Week 0) visit, Interim visits (Week 4 and Week 8), EOT (Week 12) and Follow-up (4 weeks post last dose of study drug) visits. For optimal results, the sample for androstenedione analysis should be taken between 6 am and 10 am.

Note: results of the PK and PD (biomarkers) analyses will not be disclosed to study sites to avoid unintended subject treatment unblinding (for further details refer to the XanADu Laboratory Manual).

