9.2.2 Risk/Benefit and Ethical Assessment

Xanamem™'s mechanism of action suggests a main role on hippocampal function, which may improve amnesic symptoms that are the main symptoms in subjects of mild AD. Furthermore, Xanamem™ may slow the progression of amyloid plaque deposition in the brain. Therefore, Xanamem™ has the potential for both symptomatic and disease-modifying effects in subject with mild AD.

Xanamem™ is an inhibitor of the 11β -HSD1 enzyme. Compounds which inhibit 11β -HSD1 are intended to affect the intracellular cortisone-cortisol balance, resulting in altered glucocorticoid action. It is therefore expected that AEs seen following the administration of Xanamem™ may be related to effects on glucose and fatty acid metabolism, or loss of suppression of innate immunity. In addition, inhibition of 11β -HSD1 results in enhanced cortisol clearance and potentially a compensatory increase in ACTH and cortisol secretion to maintain normal cortisol levels. As a result, ACTH-dependent secretion of adrenal androgens may be increased.

To date, Xanamem™ has an acceptable safety profile: in the MAD study²², all treatment-emergent AEs (TEAEs) were either mild or moderate in intensity. A total of 6/24 (25.0%) subjects reported at least one TEAE possibly related to study drug, whilst all the other TEAEs were reported as unrelated or unlikely to be related to study drug.

Of the five TEAEs considered to be moderate in intensity, one event of diarrhoea (20 mg UE2343) and one event of headache (35 mg UE2343) were considered as possibly related to study drug. The other moderate TEAEs were all unrelated or unlikely to be related to study drug. The laboratory parameters were within normal range and no clinically significant abnormalities were recorded. In the subsequent fed-fasted study²² in 12 subjects, the most commonly reported TEAE by preferred term was "Abnormal dreams", with a total of

five events reported by 5/12 (41.7%) subjects. These were considered possibly related to study drug (two events under fed conditions, one under fasted conditions and two across both the fed and fasted period), all mild in intensity and resolved.

Overall, there were no clinically significant abnormalities noted in nerve conduction studies for any of the subjects in the MAD cohorts.

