- 7 One PK sample will be taken 3 to 5 hours post-dose at the Baseline (Week 0) visit and two PK samples will be taken (at arrival on site [pre-dose] and 3 to 5 hours post-dose) at the Interim visits (Week 4 and Week 8). One PK sample will be taken at the EOT (Week 12) visit. NB: The subject will not be dosed during the EOT visit. For details, see [Section 9.4.1](#). The exact time-points of blood sampling for PK analysis and drug intake will be documented. Between visits, subjects will record the exact times of study drug intake in the Drug Intake Diary. The subject will be required to bring the diary to the Interim visits (Week 4 and Week 8) and EOT (Week 12) visit.
- 8 Taken from the blood sample at Baseline (Week 0), and EOT (Week 12) visits.
- 9 Women of childbearing potential only. A serum pregnancy test will be performed at Screening and a urine pregnancy test at all subsequent clinic visits.
- 10 Females only. To be taken only if there is clinical concern about the subject's menopausal status.
- 11 Urine collected for the urinalysis sample will also be used to test for the presence of benzodiazepines at the Screening visit. A second urine sample, prior to randomisation, will be needed if a benzodiazepine re-test is required.
- 12 This sample should be collected as soon as possible after the subject arrives at the study site (pre-dose). This could, if possible, be combined with other blood draws to minimise the burden for subjects. For optimal results, the sample for androstenedione analysis should be taken between 6 am and 10 am.
- 13 ECG at Baseline only required if Screening ECG was performed more than 2 weeks earlier.
- 14 Ad hoc telephone contact may occur at any time-point throughout the study, if deemed necessary by the investigator/study nurse, or if the subject wishes to report an AE. If an SAE occurs in a subject, the subject will return to the site for a PK sample. Additional procedures will be performed as indicated, for details see [Section 12.1.1.3](#)).
- 15 Cortisol will be measured using the existing PK blood samples taken at Baseline (Week 0), Week 4, Week 8, and Week 12.

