7.9 Pharmacokinetics (PK) /Pharmacodynamics (PD) Endpoints Analyses

PK plasma and PD parameters will be assessed using the PK/ PD set, respectively.

A separate Modelling and Simulation Analysis Plan will be prepared and results from the PK/PD modelling will be reported separately from the clinical study report.

XanamemTM concentrations will be summarized descriptively by treatment group, visit and time point.

PD parameters of ACTH, DHEAS, androstenedione and testosterone will be summarized for absolute values, change from baseline and % change from baseline.

Sub-group analysis will be performed by gender for PK/PD data. PK/PD data sampling details will be listed.

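### Making the hormone (PD) draw conditional on a PK sample lets a missing dose record cost a Week 4, 8 or 12 hormone sample, and conflicts with the Follow-up schedule

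*Protocol*

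**What the plan says.** Two sentences in Protocol Section 13 form a chain. The first concerns PK: "Subjects who cannot provide a documented time-point for study drug intake for the 24 hours prior to the visit will not undergo PK sampling". The second concerns the optional PD sub-study of about 50 subjects: "Subjects who cannot provide a PK sample will not undergo PD sampling". The remedy for a missed sample is: "Another attempt for PD sampling will be made at the next visit". Neither sentence says at which visits it applies.

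Protocol Section 8.5 and Table 1 schedule the PD sample at Baseline, Weeks 4 and 8, "EOT (Week 12) and Follow-up (4 weeks post last dose of study drug) visits". Section 13 requires it to be drawn pre-dose. PK samples are scheduled at Baseline and Weeks 4, 8 and 12, with none at Follow-up.

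On analysis, SAP 7.9 says that the four hormones "will be summarized for absolute values, change from baseline and % change from baseline". On the reason for measuring them, Protocol Section 9.2.2 warns that "ACTH-dependent secretion of adrenal androgens may be increased".

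**The concern.** A hormone level drawn before dosing can be assayed and summarised whether or not the subject wrote down when the last capsule was taken. Section 13 nevertheless lets a missing record remove the draw. The population has mild dementia, so missing records may go with greater impairment or poorer adherence. That link is an inference; the documents do not report it. If it holds, the on-treatment hormone data would come disproportionately from the better record-keepers.

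ACTH, DHEAS, androstenedione and testosterone are assayed nowhere else in the trial, and their possible rise is a risk that the protocol itself names. Cortisol is also measured, but from the PK samples, so the same missing record can remove it too.

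There is also a plain conflict. A site that applies Section 13 to the letter at Follow-up would have no PK sample to satisfy it, while the schedule tells the site to draw the PD sample.

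**Working it through.** The documents give no calculated figure for the PD sub-study, so there is none to reproduce. The check sets the schedule (Protocol Table 1 and its footnotes) beside the visit instructions (Sections 9.4.1.2 to 9.4.1.7).

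| PD visit | PK sample scheduled | Dose-time condition in the visit instructions |
|---|---|---|
| Baseline | Yes, 3–5 h post-dose | None |
| Week 4 | Yes, pre-dose and 3–5 h post-dose | On the pre-dose sample |
| Week 8 | Yes, pre-dose and 3–5 h post-dose | On the pre-dose sample |
| Week 12 (EOT) | Yes, one sample | Yes |
| Follow-up | No | Not applicable |

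**Visit counts.** Of 5 PD visits, 4 have a PK sample and 1 (1/5 = 20%) has none. The visit instructions attach a dose-time condition at 3.

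**Baseline.** Section 13 states: "Each participating subject will provide one blood sample between 3 to 5 hours post-dose at the Baseline (Week 0) visit". Table 1 footnote 7 agrees, and Section 9.4.1.2 attaches no last-dose condition. Applying the 24-hour rule to subjects not yet dosed would cancel a sample that the same section requires. Baseline is therefore open.

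**Weeks 4 and 8.** The scope is unclear in two ways.
- The visit instructions condition only the pre-dose PK sample, whereas Section 13 withholds PK sampling altogether. It is not stated whether a 3–5 h post-dose PK sample would satisfy the PD rule, and the PD draw comes before that sample exists.
- The visit instructions ask for the date and time of the last dose with no time limit, whereas Section 13 looks back 24 hours.

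So a missing record can cost the PD sample; the text does not settle that it always does.

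**Retry.** After a miss at Week 4 or 8, the next visit already has its own PD draw, so the missed time-point is not replaced. After a miss at Week 12, the next visit is Follow-up, four weeks after the last dose.

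**Size.** Inputs: about 50 PD subjects (Section 8.5) and 3 on-treatment PD visits, hence 50 × 3 = 150 on-treatment samples out of 50 × 5 = 250. The proportion m without a usable dose record is not given, so it is varied as an assumption. About 25 subjects on active drug assumes that the 1:1 allocation carries over to the volunteers.

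- On-treatment samples lost = 150 × m
- Subjects with Week 12 PD data = 50 × (1 − m)
- Active-arm subjects at Week 12 = 25 × (1 − m)
- Standard error relative to no loss = 1/√(1 − m), for an unchanged standard deviation

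| m (assumed) | Samples lost of 150 | Week 12, all | Week 12, active | Relative standard error |
|---|---|---|---|---|
| 10% | 15 | 45 | 22.5 | 1/√0.9 = 1.05 |
| 20% | 30 | 40 | 20 | 1/√0.8 = 1.12 |
| 30% | 45 | 35 | 17.5 | 1/√0.7 = 1.20 |

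These figures take the Baseline sample as available. They cover loss of precision only, not selection.

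**The case against.** **Dose logging does not rest on the subject's memory alone.** A diary is supplied, subjects are reminded to record each intake, the caregiver must attend every visit, and site staff review the diary. This stands. The true loss rate may be below the assumed range, and nothing in the documents fixes it.

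**Numbers can be topped up.** Under Sections 9.2 and 15.2.4 the DSMB reviews the PD data at the interim and can have further PD data collected if too few subjects on active drug contribute. This answers a shortfall in numbers. It does not answer selective loss, and it does not restore a missed Week 12 value.

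**The pairing may be deliberate.** The PD objective is the drug's effect on the hypothalamic-pituitary-adrenal axis, and Section 15.2.3.8 foresees exposure-response work, so tying each hormone value to a known recent dose has some logic. That supports flagging and, for modelling, excluding samples with unknown timing. It does not require leaving the blood undrawn, and in placebo subjects there is no exposure to tie the value to.

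**The consequences are limited.** The sub-study is optional and descriptive, and treatment is blinded, so selection would chiefly affect whom the data represent rather than the balance between arms. This stands, and it is why the point ranks as an improvement rather than a threat to the trial.

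**Follow-up is clear in practice.** A subject who is not asked for a PK sample is arguably not one who is unable to give it, and the visit instructions order the PD draw expressly. This is a fair reading. The sentence in Section 13 still has no stated scope and should be given one.

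**Conclusion.** The point holds in a limited form. At Weeks 4, 8 and 12 an undocumented dose time can remove a scheduled and consented hormone sample whose planned summary needs no dose time. The Week 12 value, once lost, cannot be replaced on drug. Section 13 and the Follow-up schedule (1 of 5 PD visits) need to be reconciled.

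Under an assumed 10–30% rate of missing records, Week 12 data fall from about 50 subjects to 45–35 and the standard error rises by about 5–20%. That rate is an assumption, and so is any link between missing records and impairment or adherence.

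A reader might infer four stronger things that the documents do not support:
- *All Baseline PD samples are blocked, so 2 of 5 visits (40%) are lost and there is no baseline for the change analysis.* A post-dose PK sample is required of each participating subject at Baseline with no last-dose condition.
- *Follow-up PD samples are forbidden.* The schedule and visit instructions order them, so this is a contradiction and not a bar.
- *Subjects are dropped from the sub-study.* One visit's sample is lost and sampling is attempted again at the next visit; the subject stays in.
- *This is the only monitoring of the named risk.* It is the only assay of these four hormones, but cortisol is also measured (from the same conditional PK samples), and adverse events are collected in all subjects.

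**What to change.** In Protocol Section 13, delete the sentence "Subjects who cannot provide a PK sample will not undergo PD sampling". State instead that PD samples are drawn at every scheduled PD visit from consenting subjects regardless of PK sampling, and that an unknown last intake time is recorded as unknown. Keep the dose-time condition for PK concentrations only. Reconcile Section 13 with Table 1 and Sections 9.4.1.2 to 9.4.1.7, so that the visits and the PK samples to which that condition applies are explicit.

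In SAP 7.9, add one line: repeat the PD summary excluding samples with unknown intake time.

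The cost is small: a few sentences in Section 13 and one line in the SAP, for blood draws already scheduled and consented. The downside is that some PD values will lack a known dose time. They are flagged, and the repeated summary shows whether they matter. Dose-timed samples remain available for exposure-response work.
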